25.4 Lost to Follow-up

A participant will be considered lost to follow-up if he or she repeatedly fails to return for scheduled visits and is unable to be contacted by the study site.

Please refer to Section [7.4](#) for actions to be taken if a participant fails to return to the clinic for a required study visit.

For handling of discontinuation of specific sites or of the study as a whole please refer to Appendix [A 9](#).

26 STUDY ASSESSMENTS AND PROCEDURES – MODULE 2

- Study procedures and their timing are summarised in the SoA (Section 19.2). Protocol waivers or exemptions are not allowed.
- Immediate safety concerns should be discussed with the Medical Monitor immediately upon occurrence or awareness to determine if the participant should continue or discontinue study intervention.
- Adherence to the study design requirements, including those specified in the SoA, is essential and required for study conduct.
- All screening evaluations must be completed and reviewed to confirm that potential participants meet all eligibility criteria. The Investigator will maintain a screening log to record details of all participants screened and to confirm eligibility or record reasons for screening failure, as applicable.
- Procedures conducted as part of the participant's routine clinical management (eg, blood count) and obtained before signing of the ICF may be utilised for screening or baseline purposes provided the procedures met the protocol-specified criteria and were performed within the time frame defined in the SoA.
- For Part A, Period 1, the amount of blood collected from each participant for the scheduled assessments, is not anticipated to exceed 440 mL in Cycle 1 (cycle duration 5 weeks), 140 mL in Cycle 2 (cycle duration 3 weeks) and 80 mL in each subsequent cycle (cycle duration 3 weeks). If a participant experiences TLS, maximum 30 mL extra blood will be collected per cycle (5 weeks) for safety reasons. **CCI**

Repeat or unscheduled samples may be taken for safety reasons or for technical issues with the samples.

- In Part A, Period 2, the amount of blood collected from each participant for the scheduled assessments, is not anticipated to exceed 350 mL in Cycle 1 (cycle duration 5 weeks), 140 mL in Cycle 2 (cycle duration 3 weeks) and 80 mL in each subsequent cycle (cycle duration 3 weeks). If a participant experiences TLS, maximum 30 mL extra blood will be collected per cycle (5 weeks) for safety reasons. **CCI**

Repeat or unscheduled samples may be taken for safety reasons or for technical issues with the samples.

26.1 Safety Assessments

26.1.1 Enrolment and Screening

At enrolment, each potential participant will provide informed consent before starting any study-specific procedures (please refer to [Appendix A](#) for Regulatory and Ethical

Considerations). Each potential participant approved for screening is assigned a unique participant enrolment number. If a participant withdraws from the study, then the enrolment number cannot be reused.

Demographic data and other characteristics will be recorded and will include date of birth, race and ethnicity, and alcohol use.

A standard medical, medication and surgical history will be obtained with review of the selection criteria with the participant. Concurrent medical signs and symptoms must be documented to establish baseline severities. Previous and concomitant treatments (coded according to the World Health Organization Drug Dictionary [WHODRUG]) will be collected for each participant. A disease history, including the date of initial diagnosis, staging within 30 days of first dose of AZD4573, prognostic indices/disease profiling for MCL (derived from local laboratory results) and list of all prior anti-cancer treatments, and responses and DoR to these treatments, will also be recorded.

Each participant will undergo screening (see Section 19.2) during the 30 days before admission to confirm eligibility (see Sections 23.1 and 23.2).

26.1.2 Physical Examinations

A complete physical examination, including a standard neurological examination should be completed at Screening and will include, at a minimum: the general appearance of the participant, height, weight, and examination of the skin, eyes, ears, nose, throat, lungs, heart, abdomen, extremities, musculoskeletal system, lymphatic system, and nervous system. Investigators should pay special attention to clinical signs related to previous serious illnesses and new or worsening abnormalities may qualify as AEs.

Symptom-directed physical exams are done thereafter for each dosing day as outlined in the SoA, including the SFU visit (Section 19.2) in Period 1 and Period 2.

26.1.3 Vital Signs

Vital signs will be performed at timepoints specified in the SoA (Section 19.2).

Changes from baseline abnormalities should be recorded in participant notes. New or worsened clinically significant abnormalities should be recorded as AEs on the Adverse Event eCRF.

Pulse rate and blood pressure

Blood pressure and pulse/heart rate measurements will be assessed with a completely automated device. Manual techniques will be used only if an automated device is not

available.

Blood pressure and pulse measurements should be preceded by at least 10 minutes of rest for the participant in a quiet setting.

Pulse rate and blood pressure measurement timepoints are:

- Screening

Period 1 and Period 2

- Cycle 1 (Weeks 1 to 3):
 - Predose (up to 2 hours prior to infusion)
 - 1 hour after the start of the infusion (\pm 10 minutes)
 - At the end of the infusion (up to 10 minutes post dose)
 - 4 hours after the start of the infusion (\pm 30 minutes)
 - 6 hours after the start of the infusion (\pm 30 minutes)
- From Cycle 1 Week 4 onwards:
 - Predose (up to 30 minutes prior to infusion)
 - At the end of the infusion (up to 30 minutes post dose) on each dosing day
- 30-Day SFU

Body temperature

Body temperature will be measured in degrees Celsius at the following timepoints in Period 1 and Period 2:

- Predose (up to 2 hours prior to all infusions)

Weight

Weight will be measured in kilograms at the following times:

- Screening

Period 1 and Period 2

- Cycle 1 (weeks 1-3) predose
- Cycle 1 Week 4 onwards, Day 1 of each cycle predose

- 30-Day SFU

26.1.4 Electrocardiograms (ECGs)

ECG will be performed at timepoints specified in the SoA (Section [19.2](#)).

Twelve-lead ECGs will be obtained after the participant has been resting semi-supine for at least 10 minutes before the times indicated. All ECGs should be recorded with the participant in the same physical position where possible.

If an abnormal ECG finding at Screening or baseline is considered to be clinically significant by the Investigator, it should be reported as a concurrent condition. If a clinically significant abnormal ECG finding occurs on study, contact the Medical Monitor.

Single ECGs will be collected for local and central analysis at the following timepoints:

- Screening

Period 1 and Period 2

- Cycle 1, Weeks 1 through 5, and Cycle 2, Day 1:
 - Predose (at the day of infusion prior to infusion)
 - End of infusion (within 30 minutes of end of infusion)
- Cycles 3+ Day 1 of each cycle:
 - Within 30 minutes after the end of infusion
- 30-Day SFU

Any abnormal finding in the ECG tracing will be evaluated by the Investigator and will be specifically documented and registered in the eCRF. Throughout the study, clinically relevant new findings or worsening of a pre-existing finding in the ECGs (parameters or abnormal findings in the tracing) must be considered an AE and must be recorded in the AE CRF form.

If an unscheduled ECG is done at any time, then an electrolyte panel (ie, calcium, magnesium, potassium), and troponin I/troponin T must be done to coincide with the ECG testing. Note: either a troponin I or troponin T assay can be used per SoC at the respective hospital. If the hospital has both a SoC troponin I and troponin T assay available, the investigator shall use only one consistently for the duration of the study.

26.1.5 WHO/ECOG Performance Status

ECOG performance status will be assessed at the following times (see Section [19.2](#)):

- Screening

Period 1 and Period 2

- Cycle 1 through Cycle 8:
 - Predose each dose of AZD4573
- Cycles 9+, Day 1 of each cycle:
 - Predose each dose of AZD4573
- 30-day SFU

Performance status should be measured using the ECOG Performance Status Scale ([Table 33](#)). It is recommended, where possible, that a participant's performance status be assessed by the same person throughout the study.

Table 33 ECOG Performance Status Scale

Grade	Description
0	Fully active, able to carry on all pre-disease performance without restriction
1	Restricted in physically strenuous activity but ambulatory and able to carry out work of a light or sedentary nature, eg, light housework, office work
2	Ambulatory and capable of all selfcare but unable to carry out any work activities; up and about more than 50% of waking hours
3	Capable of only limited selfcare; confined to bed or chair more than 50% of waking hours
4	Completely disabled; cannot carry on any selfcare; totally confined to bed or chair
5	Dead

26.1.6 B Symptoms

Information on B symptoms (eg, unintentional weight loss, fevers, and night sweats) will be collected at the following times ([Section 19.2](#)).

- Screening

Period 1 and Period 2

- Cycle 1 through Cycle 8:
 - Predose AZD4573
- Cycles 9+, Day 1 of each cycle:

- Predose AZD4573
- 30-day SFU

26.1.7 Clinical Safety Laboratory Assessments

For all participants, results of safety laboratory testing (haematology and clinical chemistry at a minimum) must be available within 72 hours prior to dosing and must be reviewed by the Investigator prior to administration of AZD4573 (all cohorts). If clinically indicated, additional clinical laboratory tests and evaluations may be performed by the Investigator (eg, additional haematology/clinical chemistry panels, TLS parameters, liver enzyme tests); these need to be entered into the eCRF.

This study will use local laboratories.

The following laboratory variables will be measured in Period 1 and Period 2.

Haematology: complete blood count (CBC) with automated and/or manual differential including, but not limited to, white blood cell count, haemoglobin, haematocrit, platelet count, ANC, and absolute lymphocyte count (ALC), and blast cells. Haematology should be evaluated before dosing while participants are receiving treatment.

Haematology samples will be collected at the following timepoints:

- Screening

Period 1 and Period 2

- Cycles 1, 2, and 3
 - Predose AZD4573 (within 72 hours prior to infusion)
 - 24 hours after the start of the infusion
- Cycles 4+
 - Predose AZD4573 (within 72 hours prior to infusion)
 - If clinically indicated, 24-hour after the start of the infusion
- 30-day SFU

The Investigator may take additional, unscheduled samples throughout the study if deemed clinically warranted and these need to be entered into the eCRF.

Haematology tests do not need to be repeated before first dose if the first-dose visit is within 3 days of the Screening sample.

Clinical Chemistry: albumin, chloride, bicarbonate, calcium total, magnesium, phosphorous, glucose (fasting preferred), CK, ALP, ALT, ammonia (where available at local institution; to be tested every 2 weeks), AST, urea, cholesterol, C-reactive protein, creatinine, Factor V (where available at local institution), GGT, lactate dehydrogenase (LDH), phosphate, potassium, sodium, triglycerides, total bilirubin, direct and indirect bilirubin, total protein, uric acid.

Clinical chemistry samples will be collected at the following timepoints:

- Screening

Period 1 and Period 2

- Cycles 1, 2, and 3
 - Predose AZD4573 (within 72 hours prior to infusion)
 - 24 hours after the start of the infusion
- Cycles 4+
 - Predose AZD4573 (within 72 hours prior to infusion)
 - If clinically indicated, 24-hour after the start of the infusion
- 30-Day SFU

The Investigator may take additional, unscheduled samples throughout the study if deemed clinically warranted and these need to be entered into the eCRF.

Clinical chemistry and haematology tests do not need to be repeated before first dose if the first-dose visit is within 3 days of the Screening sample.

In addition, GLDH and CPK will be measured at Screening for all participants. If GLDH cannot be performed locally, LDH will be analysed locally and a serum sample must be collected for central retrospective GLDH analysis, which will be performed as applicable. Refer to the Laboratory Manual for details.

Coagulation testing includes aPTT (partial thromboplastin time)/PT (prothrombin time), INR, D-dimer (where available at institution), and fibrinogen.

Samples for coagulation testing will be collected at the following timepoints:

- Screening

Period 1 and Period 2

- Cycles 1, 2, and 3
 - Predose AZD4573 (within 72 hours prior to infusion)
 - 24 hours post-infusion
- Cycles 4 through 8
 - Predose AZD4573 (within 72 hours prior to infusion)
 - If clinically indicated, 24-hour after the start of the infusion
- Cycles 9+, on Day 1 of each cycle
 - Predose AZD4573 (within 72 hours prior to infusion)
- 30-Day SFU

The Investigator may take additional, unscheduled samples throughout the study if deemed clinically warranted and these need to be entered into the eCRF.

Urinalysis: pH, ketones, specific gravity, bilirubin, protein, blood, and glucose. On dosing days, urinalysis should be performed at the following timepoints:

- Screening

Period 1 and Period 2

- Cycles 1 through Cycle 8
 - Predose AZD4573 (within 72 hours prior to infusion)
 - Within approximately 2 hours after the end of the infusion
- Cycles 9+, on Day 1 of each cycle
 - Predose AZD4573 (within 72 hours prior to infusion)
 - Within approximately 2 hours after the end of the infusion
- 30-Day SFU

Cardiac troponin I or troponin T measurements (note: either a troponin I or troponin T assay can be used per SoC at the respective hospital. If the hospital has both a SoC troponin I and troponin T assay available, the investigator shall use only one consistently for the duration of the study.) are required at the following timepoints:

- Screening

Period 1 and Period 2

- Cycle 1, Weeks 1 through 5
 - Predose AZD4573 (within 72 hours prior to infusion)
 - 24 hours post start of the infusion
- Cycles 2+ Day 1 of each cycle
 - Predose (within 72 hours prior to infusion)
- 30-Day SFU

Electrolyte panel: sodium, chloride, calcium, magnesium, potassium.

If an unscheduled ECG is done at any time, then an electrolyte panel (ie, calcium, magnesium, potassium), and troponin must be done to coincide with the ECG testing.

Supra-renal glands: T4, cortisol, adrenocorticotrophic hormone (ACTH) and thyroid-stimulating hormone (TSH) should be measured at the following timepoints:

- Screening

Period 1 and Period 2

- Cycle 2, Day 1
 - Predose AZD4573 (within 72 hours prior to infusion)
- 30-Day SFU

Pancreas: Lipase and amylase measurements are required at the following timepoints:

- Screening

Period 1 and Period 2

- Cycles 1 through 8:
 - Predose AZD4573 (within 72 hours prior to infusion)

- Cycles 9+, on Day 1 of each Cycle:
 - Predose AZD4573 (within 72 hours prior to infusion)
- 30-Day SFU

Lipase/amylase tests do not need to be repeated before first dose if the first-dose visit is within 3 days of the Screening sample.

TLS monitoring will include: potassium, calcium, phosphate, uric acid, and creatinine. TLS monitoring will be performed at the following timepoints:

Period 1 and Period 2

- Cycle 1, Weeks 1 through 3
 - Predose AZD4573
 - 6 hours (\pm 30 minutes) after the start of the infusion
 - 24 hours (\pm 1 hour) after the start of the infusion (and prior to acalabrutinib dosing in Period 2)

Participants showing signs of clinical or laboratory TLS at 6 hours after the start of the infusion must be admitted for in-patient TLS monitoring for a minimum of 24 hours after the start of the infusion and monitored every 4 to 6 hours during this time (or more frequently if clinically indicated).

For each TLS monitoring timepoint, a TLS Monitoring page in the eCRF is to be filled out.

Liver chemistry tests: For any participant on study who experiences elevated ALT /AST $\geq 3 \times$ ULN and/or elevated total bilirubin $\geq 2 \times$ ULN: repeated liver chemistry tests (INR, fibrinogen, D-dimer [where available at institution], ALP, ALT, AST, GLDH, CPK, total bilirubin, direct bilirubin, indirect bilirubin) are required at 48 hours (-2/+12 hours) and 96 hours (-2/+12 hours) after the start of the infusion and until resolution of the event. However, in case the event is not resolved within 96 hours the medical monitor should be contacted. If GLDH cannot be performed locally, LDH will be analysed locally and a serum sample must be collected for central retrospective GLDH analysis. Refer to the Laboratory Manual for details.

During the course of the study the Investigator will remain vigilant for increases in liver biochemistry. The Investigator is responsible for determining whether a participant meets PHL criteria at any point during the study. The Investigator participates, together with the

Sponsor, in review and assessment of these cases. Hy's Law (HL) criteria are met if there is no alternative explanation for the elevations in transaminases and total bilirubin levels.

If an unscheduled ECG is done at any time: troponin and an electrolyte panel* must be done to coincide with the ECG testing.

* can include: sodium, calcium, potassium, chloride, phosphate, magnesium.

If a participant is assessed as meeting PHL criteria, please refer to [Appendix E](#).

Hepatitis serology will be conducted at Screening. Hepatitis serology must include hepatitis B surface antigen (HbsAg), hepatitis B surface antibody (anti-HBs), anti-HBc, and hepatitis C (HCV) antibody. Participants who are anti-HBc positive, or have a known history of hepatitis B virus (HBV) infection, should be monitored every 3 months with a quantitative PCR test for HBV DNA (Section [17.1.10.4](#)). In addition, any participants testing positive for any hepatitis serology must have PCR testing for verification purposes.

Pregnancy: a sample for a pregnancy test will be collected from all female participants of childbearing potential at:

- Screening (serum)
- Cycle 1, Week 1:
 - Predose
- Cycles 2+: once every 21 days (\pm 7 days) prior to initiating a new cycle
- 30-day SFU

Pregnancy tests after Screening may be serum or urine. Urine β -hCG and quantitative serum β -hCG tests are permitted. If a urine β -hCG test is positive or indeterminate, quantitative serum β -hCG will be performed for confirmation. Additional testing may be performed at Investigator discretion for example in the event of suspected contraception failure.

CMV: All subjects will have CMV testing at Screening including serology testing for CMV immunoglobulin (Ig)G and CMV IgM and CMV DNA PCR testing. Subjects must have a negative result for CMV DNA PCR such that CMV DNA is not detected by PCR at Screening, to be eligible for the study. The Screening CMV serologies will be advisory only, to guide investigators in assessing the risk of new infection or reactivation of CMV while on study.

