Bone marrow biopsy & aspirate ^{cc}										As clinically indicated and to confirm CR				Section 26.4.3 and Section 26.10.3				
Disease assessment ^a and radiologic scans ^{dd}	See Table 38 schedule										X			Section 26.4.2				
AZD4573 intravenous ^{ee}	Once weekly (from Cycle 1, Week 1 to end of treatment) ^{jj}													Section 24.1				
Acalabrutinib oral, BID ^{ff}	Twice daily (from Cycle 1, Week 1 to end of treatment)													Section 24.1				
Acalabrutinib drug accountability ^{gg}	X	X	X	X	X	X	X	X	X					Section 24.5				
Disease progression follow-up (SoC)												X		Section 26.1.9.2				
Survival Follow-up												X		Section 26.1.9.3				

- ^a Disease assessments will be done by the Investigator using the Lugano Response Criteria for Non-Hodgkin's Lymphoma ([Cheson et al 2014](#)). Additional disease assessments may be performed as clinically indicated.
- ^b The SFU visit will be performed 30 days (± 7 days) after the last dose of all study drug. Tumour assessments will be repeated at this visit if they have not been performed within 9 weeks if the participant discontinued before or during Week 26, or 12 weeks if the participant discontinued after Week 26.
- ^c Vital signs (blood pressure, pulse rate, temperature) will be assessed after the participant has rested for at least 10 mins. Blood pressure and pulse rate will be measured on Day 1 of Cycle 1, Weeks 1-3 at the following timepoints: predose (up to 2 h prior to infusion), 1 h after the start of the infusion (± 10 mins), at end of infusion (up to 10 mins post dose) and then 4 h (± 30 mins) and 6 h (± 30 mins) after start of infusion, from Cycle 1 Week 4, at predose (up to 30 mins prior to infusion), at the end of infusion (up to 30 mins post dose), and at the 30-day SFU. Temperature to be taken pre-infusion (up to 2 h prior to all infusions).
- ^d As the study is intended to recruit adults, height should only be measured at Screening. Weight to be measured prior to infusions on Day 1 of each cycle, and at the 30-day SFU visit.
- ^e Participants should be in semi-supine position and resting for ≥ 10 mins before the ECGs. Single ECGs for local and central analysis are required at the following timepoints: for Cycle 1, Weeks 1-5 and Cycle 2 Day 1 predose (at the day of infusion prior to infusion) and within 30 mins of the end of infusion; for Cycles 3+ on Day 1 within 30 mins after the end of infusion, and at the 30-day SFU visit.

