- ^k Clinical chemistry should be measured at Cycles 1, 2, and 3 predose (within 72 h prior to infusion), and 24 h post-infusion of AZD4573. From Cycle 4 onwards, clinical chemistry testing should be measured predose (within 72 h prior to infusion) and (if clinically indicated) 24 h after the start of the infusion. A sample will also be drawn at the 30-day SFU. The investigator may take additional, unscheduled samples throughout the study if deemed clinically warranted and these need to be entered into the eCRF. Clinical chemistry tests do not need to be repeated before first dose if the first-dose visit is within 3 days of the most recently available sample. In addition, GLDH and CPK will be measured before the first dose in Period 2 for all participants. If GLDH cannot be performed locally, LDH will be analysed locally and a serum sample must be collected for central retrospective GLDH analysis, which will be performed as applicable. Refer to the Laboratory Manual for details. If an unscheduled ECG is done at any time, then an electrolyte panel (ie, calcium, magnesium, potassium) and troponin must be done to coincide with the ECG testing.
- ^l Urine samples will be collected at the following timepoints: Cycles 1-8, predose AZD4573 (within 72 hours prior to infusion) and within approximately 2 hours after the end of infusion, Cycles 9+ on Day 1 of each cycle, predose AZD4573 and within approximately 2 hours after the end of infusion, and at the 30-day SFU.
- ^m Pregnancy test to be performed once every 21 days (± 7 days) prior to initiating a new cycle and at the 30-day SFU visit (serum or urine). Additional testing may be performed at Investigator discretion (eg, in the event of suspected contraception failure).

- n Lipase and amylase should be evaluated at Cycles 1-8 predose AZD4573 (within 72 hours prior to infusion), Cycles 9+, predose AZD4573 (within 72 hours prior to infusion) on Day 1 of each cycle, and at the 30-day SFU visit.
- o Participants who are anti-HBc positive, or have a known history of HBV infection, should be monitored every 3 months with a quantitative PCR test for HBV DNA. Any participants testing positive for any hepatitis serology must have PCR testing for verification purposes.
- p CD4, CD8, CD19, CD16/NK and serum immunoglobulins (IgA, IgM, IgG) will be drawn at Day 1 (predose) of Cycles 2, 4, 7, 9, 13, 16, 19 and every 6 months thereafter (predose), and at the 30-day SFU.

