26.1.8 Other Safety Assessments

Monitoring for TLS per the SoA (Section [19.2](#)) and prophylaxis for TLS are outlined in detail in Section [26.1.10.10](#).

Blood samples for **CCI** [REDACTED] will be collected per the SoA (Section 19.2) and as outlined in Section 26.1.7.

Additional safety assessment requirements include:

- **Echocardiograms (ECHOs):** In addition to Screening, an ECHO should be done within 14 days after an abnormal ECG finding (eg, T-wave inversion/flattening) or as soon as possible when clinically indicated. If an ECHO cannot be taken, a multigated acquisition (MUGA) scan to assess left ventricular ejection fraction (LVEF) will be done. In case of any T-wave abnormality, the ECHO (or MUGA) should be repeated at the 30-day SFU visit to address the question of recovery, during the off-treatment period.
- **CD4, CD8, CD19, CD16/NK** cell count and serum immunoglobulins (IgA, IgM, IgG):
 - Screening
 - Day 1 of Cycles 2, 4, 7, 9, 13, 16, 19
 - Predose
 - Every 6 months thereafter (predose)
 - 30-Day SFU

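### Section 26.1.7 requires TLS monitoring in Period 2 Cycle 1 Weeks 1 to 3, but Table 24, the Period 2 schedule, has no TLS row and no laboratory draw at 6 hours

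*Protocol*

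**What the plan says.** Section 26.1.7 names five analytes for TLS monitoring and introduces the sampling times: "TLS monitoring will include: potassium, calcium, phosphate, uric acid, and creatinine. TLS monitoring will be performed at the following timepoints". The list is headed for both periods and covers Cycle 1 Weeks 1 to 3: predose, 6 h (± 30 min) and 24 h (± 1 h). The 24 h entry carries a condition that can apply only in Period 2: "after the start of the infusion (and prior to acalabrutinib dosing in Period 2". The 6 h result has a consequence: "Participants showing signs of clinical or laboratory TLS at 6 hours after the start of the infusion must be admitted for in-patient TLS monitoring". Each timepoint also needs its own eCRF page.

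Section 26.1.8 places this monitoring in the schedule: "Monitoring for TLS per the SoA" (Section 19.2). It refers to Section 26.1.10.10 for detail. The opening list of Section 26 says that the schedule summarises procedures, and adds: "Adherence to the study design requirements, including those specified in the SoA, is essential and required for study conduct".

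Table 23 (Period 1) has a TLS row on Days 1, 8 and 15, with footnote o. Table 24 (Period 2) has neither row nor footnote.

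Section 26.1.10.10.3 requires monitoring for up to 24 h after each dose until at least one dose at target level has been given, that is, for at least the first three weekly doses. Section 22.1 says that participants will have reached 12 mg in Period 1, so Period 2 needs no new ramp-up. The note to Table 29 starts Period 2 whenever progressive disease occurs during monotherapy.

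**The concern.** Two current safety instructions differ on whether a participant has TLS bloods taken at 6 h in the first three weeks of combination treatment. A site working from Table 24 omits draws that Section 26.1.7 makes mandatory. A site working from Section 26.1.7 takes draws, and completes eCRF pages, that its schedule does not list.

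The 6 h draw matters most because it decides admission. Period 2 is also when acalabrutinib is added. Section 26.1.10.10 calls TLS an identified risk of that drug, and Section 20.3.1 lists TLS among the potential overlapping toxicities of the pair. If the sponsor holds that tolerance of AZD4573 alone makes further monitoring unnecessary, that reasoning should be stated, not left to be read from a missing row.

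The point concerns safety conduct and consistency of safety data. It touches no sample size, estimate or test.

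**Working it through.** **1. Is the row really absent?** In Table 23 the order is clinical chemistry (footnote n), TLS monitoring (o), urinalysis (p). In Table 24 it is clinical chemistry (k), then urinalysis (l). The letters run on without a gap, so no row was lost when the text was extracted. Within Table 24 and its notes, TLS appears only in the abbreviation list.

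**2. Timepoints per participant, Period 2 Cycle 1**
- Section 26.1.7: 3 timepoints × 3 weeks = 9.
- TLS entries in Table 24: 0.
- Timepoints with a possible chemistry counterpart (predose, 24 h): 2 × 3 = 6.
- Timepoints with none (6 h): 1 × 3 = 3.

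**3. How good is the chemistry counterpart?** The chemistry panel in Section 26.1.7 contains all five TLS analytes. Table 24 footnote k begins: "Clinical chemistry should be measured at Cycles 1, 2, and 3 predose". It allows the predose sample up to 72 h before infusion and times the second sample 24 h after the infusion. The infusion lasts 2 h. Counted from its end, the draw falls at 24 + 2 = 26 h from the start, outside the TLS window of 24 ± 1 = 23 to 25 h. Section 26.1.7 times the same chemistry draw from the start of infusion, which would fit. Footnote k does not require sampling before acalabrutinib. So six of the nine are covered approximately at best.

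**4. What is scheduled at 6 h?** Vital signs only. Footnote c has, for Cycle 1 Weeks 1 to 3, "6 h (± 30 mins) after start of infusion, from Cycle 1 Week 4, at predose" (the last words begin the later-visit rule).

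**5. Which text is the outlier?**

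| Source | Routine TLS monitoring in Period 2? |
|---|---|
| Section 26.1.7 | Yes, Cycle 1 Weeks 1 to 3 |
| Table 24 | None listed |
| Section 26.1.10.10.3, target-level dose already given | Minimum already met |
| Section 26.1.10.10.3, no target-level dose yet | Yes |

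The Period 1 ramp is 6 mg, 9 mg, then 12 mg from Day 15. A participant who progresses before Day 15 can enter Period 2 without a target-level dose. The first scheduled scan is after 8 weeks (Table 37), so this needs an unscheduled finding of progression. It is uncommon but permitted. For such a participant Table 24 conflicts with Section 26.1.10.10.3 as well as with Section 26.1.7.

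**6. Number affected.** The protocol gives no count. The plan was about 12 participants in Module 2 (Section 27.2), so the ceiling is about 12 × 3 = 36 six-hour draws if all entered Period 2. The floor is zero: Section 18.5 reports that enrolment was permanently halted, and Section 22 keeps Module 2 closed until the Module 1 RP2D is set.

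**The case against.** The strongest reply is that Table 24 is right. Section 26.1.8 points to Section 26.1.10.10, whose rule is normally satisfied in Period 1, and Section 22.1 explains why no ramp-up recurs. On that reading Section 26.1.7 is a list not trimmed for Period 2, and a site that follows it only draws extra blood. This is plausible and may be the sponsor's intent. It does not remove the conflict: Section 26.1.7 would then be wrong as written, its Period 2 condition on the 24 h draw shows more than a shared heading, and the early-progression case stays uncovered.

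A reader might infer that the 6 h draw is unscheduled, or that the admission rule is switched off in Period 2. The documents do not support that. Section 26.1.7 itself prescribes the draw and the admission; what is missing is the entry in Table 24, and the trigger fails only where a site works from the table alone.

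A reader might also infer that participants are unprotected in Period 2. They are not. Prophylaxis is mandatory for all infusions (Section 26.1.10.10.1) and IV saline for all participants (26.1.10.10.2). Uric acid must be below ULN before each infusion, and suspected TLS means hospital stay and treatment (26.1.10.10.3). Table 31 has TLS dosing rules for both drugs. Vital signs are taken at 4 h and 6 h, and TLS parameters can be added when clinically indicated.

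The Period 2 blood-volume allowance cannot show that routine monitoring was planned. It reads "If a participant experiences TLS, maximum 30 mL extra blood will be collected per cycle (5 weeks) for safety reasons", so it covers only participants in whom TLS occurs.

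**Conclusion.** The inconsistency stands: nine required Period 2 timepoints against none in the schedule, three of them without any laboratory draw nearby. The documents do not settle which text is wrong. Section 26.1.7 may be the outlier for anyone who reached 12 mg in Period 1; Table 24 is incomplete for anyone who did not. Correction is worthwhile because the disputed draw triggers mandatory admission, but the practical reach is limited to participants who have not completed Period 2 Cycle 1 Week 3, possibly none.

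This assumes that the core sections of the protocol, which were not available for this check, set no order of precedence between the schedule and the body text. The sections on Module 2 set none for this point.

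**What to change.** Choose one of two edits.

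- **Period 2 monitoring is intended.** Add a TLS monitoring row to Table 24 for Cycle 1 Days 1, 8 and 15. Its footnote should give predose, 6 h ± 30 min, and 24 h ± 1 h after the start of infusion, the last before acalabrutinib. Amend Section 26.1.10.10.3 to say that monitoring applies again in these weeks.
- **It is not intended.** Delete Period 2 from the TLS list in Section 26.1.7 and state the rationale. Keep monitoring, with a conditional footnote in Table 24, for anyone who enters Period 2 without a prior target-level dose.

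Both are text edits. The first adds three draws per participant to what Table 24 lists, though Section 26.1.7 already requires them. It needs no extra visit, since 6 h vital signs are due in all three weeks. In Weeks 1 and 3 the TLS window (5.5 to 6.5 h) overlaps the PK window (7 ± 1 h, or 6.0 to 8.0 h) between 6.0 and 6.5 h, so one venepuncture can serve both. Only the Week 2 draw is separate.
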